The proposed sample of 150 participants is based on a power calculation with clusters of approximately five participants from each of the 30 municipalities. Based on a previous trial, a minimal clinically important average difference on the PGSI scale is set to 2 points between intervention and control group with a standard deviation (SD) for change of 2.83 in each group (40). To observe a statistically significant difference with a power of 80%, an intra-cluster (municipality) correlation coefficient (ICC) of 10% and an estimated attrition rate of 25% for the primary outcome at three months, we will need approximately 150 participants. We assume a high attrition rate since the participants are at high risk for acute institutionalisation (see inclusion criteria).

This trial must perform cluster randomisation, with the municipality as the cluster, for two main reasons. The intervention is a biopsychosocial intervention that involves the entire interdisciplinary team and staff in the home care services of the participating municipalities to optimize the approach towards a group of patients in the municipalities. In addition, without cluster randomisation, the study runs the risk of transmitting all or parts of the intervention model to the individual control patients in the same municipalities (42). The patients in the control group will receive care and treatment as usual, but they will probably also profit from the extra attention given by the home care services because of their participation in the RCT and because of the use of the measure for the primary outcome, the PGSI. In this way, we can isolate any effects on goal achievements to prevent or resolve crises to the main difference between IMs and CMs, i.e., the TIME intervention.

RQ3 Selection of participants for the individual in-depth interviews

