responsibility in the trial. Before randomisation, these nurses will complete a one-day educational course on the procedures for the trial. Their main task will be to recruit participants according to the inclusion criteria, obtain written consent for participation, and facilitate the interviews for the assessments of the participants at baseline, three months, and six months. The manager of the home care services will select these nurses in the municipality based on the following criteria: health care professionals who work on a nearly full-time basis, have shown interest in professional development and have gained legitimacy with the rest of the staff. Thus, these health care professionals can be selected among registered nurses, auxiliary nurses, or members of other professional groups (e.g., social workers or occupational therapists) in home care services.

After this coeducational session for both the IMs and CMs, the CMs will continue care and treatment as usual (CTAU). Care and treatment as usual will usually involve medication follow-up and medical procedures, personal care, dressing, and bathroom assistance.

Specific education and training of staff in the IMs

The staff in the IMs will complete four hours of lectures, training and role-play related to TIME. The educational program is aimed at as many employees as possible in the organization and provides basic knowledge about the TIME model. The education and training team will consist of eight specialist registered health care professionals in geriatrics or geriatric psychiatry and one physician with special competence in nursing home medicine. All members of the education and training team are familiar with TIME and have used the model for some years in real-world clinical settings. The lectures will be standardized according to the steps listed in the TIME manual.

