Specially trained nurses (data assessors) from the project's research centre who are not affiliated with the municipalities will, together with staff members in the home care services, assess patients' baseline characteristics before randomisation. These data assessors will after randomisation be blinded to the randomisation result. They will assess the effect of the intervention via telephone by interviewing the participants, the next of kin and the staff members who know the patient best, at three months and six months after baseline assessments. All assessors are nurses with substantial experience and formal training on the use of the assessment scales. They will attend a one-day course on the use of the assessments scales before start of the trial. A description of the questionnaires, including data assessors, respondents and the time point(s) at which they are administered, is provided in Table 1.

Baseline data and primary and secondary outcome measures

The primary outcome of the trial is the difference in the change between the intervention and control groups in individual goal achievement to resolve or alleviate the challenges regarding crises between baseline and three months using the PGSI (scale of 1–10) (34). We chose this primary outcome because there is a need for a targeted outcome that comprises the variability in a heterogeneous population. It is very unlikely that a participant would be harmed due to participation in the RCT; therefore, it is not deemed necessary to have a harm outcome in the study. In the RCT, no new experimental treatments for the patients will be introduced, and care and all treatment actions will rely on recommended national care and treatment guidelines.

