The data will be presented as frequencies and percentages for categorical and means (standard deviations) for the continuous variables. The normality of continuous variables will be assessed graphically. If necessary, skewed data will be transformed. Differences in the changes in outcomes between the intervention group and the control group will be assessed by a linear mixed model with fixed effects for time component and group and the interaction between the two. The analysis will be performed as an intention-to-treat analysis. A significant interaction will imply the differences in change between the groups. Random effects for patients nested within municipalities and slopes (if significant) will be included into the model. Individual time point contrasts will be derived within each group at each time point with the corresponding 95% confidence intervals and p-values. Linear mixed model correctly adjusts estimates for intra-cluster correlations as well as for intra-individual correlations due to repeated measurements in time. The model also handles unbalanced data by allowing inclusion of all available information, also from dropouts. The analyses for primary and secondary outcomes will be adjusted for baseline PGSI-scores, baseline severity of dementia (Clinical Dementia Rating), and age of the participants.

For RQ2 the dependent variables will be the changes from baseline in primary or secondary outcomes that are statistically significant after the implementation of TIME. Independent variables will be participants characteristics from the RCT, and organizational data (staff characteristics and organizational data) assessed in the process evaluation study in WP3.

Data analysis of qualitative data for RQ3

For the analysis, thematic content analysis will be used. Thematic content analysis is a method with the purpose to identify, analyse, and report patterns and themes in qualitative data (59, 60). The aim is to provide a systematic description of both the manifest and latent content of the data, and in the

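### Keeping slopes only when significant can leave municipality clustering of change out of the primary standard error, if baseline is an outcome row and the planned 10% ICC is that of change

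*Protocol*

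**What the plan says.** The Protocol section on data processing and statistical analysis for RQ1 and RQ2 specifies a linear mixed model with time, group and their interaction. The treatment effect is read from the interaction: "A significant interaction will imply the differences in change between the groups". On the random part it says "Random effects for patients nested within municipalities and slopes (if significant) will be included into the model". The nested intercepts are therefore unconditional and the slopes conditional. No retention threshold is given, and no level (patient or municipality) for the slopes. The section then asserts: "Linear mixed model correctly adjusts estimates for intra-cluster correlations as well as for intra-individual correlations due to repeated measurements in time". It also says: "The analyses for primary and secondary outcomes will be adjusted for baseline PGSI-scores".

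Three other places bear on this:

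- The section on baseline data and outcome measures: "The primary outcome of the trial is the difference in the change between the intervention and control groups in individual goal achievement", from baseline to three months.
- The section on staff education and training, on the project nurses' task: "facilitate the interviews for the assessments of the participants at baseline, three months, and six months". Table 3 likewise shows PGSI at all three visits.
- The sample size section plans with a "standard deviation (SD) for change of 2.83 in each group", and with "an intra-cluster (municipality) correlation coefficient (ICC) of 10% and an estimated attrition rate of 25% for the primary outcome at three months". It names the municipality as the unit of randomisation.

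**The concern.** The sample size allows for correlation within municipalities, and the standard error of the primary contrast should carry the same allowance. In a model with baseline as an outcome row, a municipality intercept describes a level that is the same at every visit, so it drops out of any within-patient change. Only a term that lets municipalities differ in their change (a municipality slope or a municipality-by-time effect) brings clustering into the interaction's standard error. The only such term the protocol mentions is the one it makes depend on significance. With 30 municipalities of four or five patients, non-significance says little about whether clustering is absent. When the term is dropped, the interaction is tested as if patients had been randomised individually, and the confidence interval is too narrow.

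**Working it through.** **Inputs from the sample size section.** 30 municipalities; about 5 patients each, so 5 × 0.75 = 3.75 after attrition; difference 2 points; SD of change 2.83; ICC 0.10; power 80%. **Assumed, because not stated:** two-sided 5% alpha and a 5% threshold for keeping the term (others tried below).

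**The plan's own figure.** Per arm, 2 × (1.96 + 0.84)² × 2.83² / 2² = 31.4, so 32. The design effect 1 + 4 × 0.10 = 1.4 gives 44.8, so 45 per arm and 90 in total; 90/0.75 = 120. The stated inputs thus give about 120, not 150. The plan is conservative here, and the present point does not depend on it.

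**Which rows are outcomes.** With rows at 3 and 6 months only, the interaction would test change from 3 to 6 months, which is not the primary outcome. The interaction test fits the primary outcome best if baseline is a row. The adjustment for baseline PGSI keeps this from being certain.

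**What cancels.** Write Y = fixed part + u (municipality) + p (patient) + v (municipality-by-visit) + e. The 3-month change is then fixed part + (v₃ − v₀) + (e₃ − e₀); u and p are gone. A generalised least squares check with assumed variances agrees. With baseline as a row, raising the municipality intercept variance from 0 to 1.6 leaves the interaction's standard error at 0.413, while a municipality slope variance of 0.8 raises it to 0.527. With post-baseline rows only, the same intercept variances raise the standard error from 0.372 to 0.593, so clustering then enters without any slope.

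**Standard error at stake.** Omitting the term understates the standard error by √(1 + (m − 1) × 0.10): √1.275 = 1.13 at m = 3.75 and √1.4 = 1.18 at m = 5.

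**Chance that the term is kept (change scores).** The between-municipality F test has 28 and 30(m − 1) df, and under the ICC the F ratio is scaled by (1 + (m − 1) × 0.10)/0.90. For m = 3.75, 4 and 5 the scale is 1.417, 1.444 and 1.556, and power is 31.8%, 34.7% and 46.3%.

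**Type I error (change scores).** 200,000 simulated null trials per setting. If the term is kept: t test on municipality means, 28 df. If dropped: patient-level t test.

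| Patients per municipality | Kept | Rule | Rule, 28 df in both branches | Always fitted | Never fitted |
|---|---|---|---|---|---|
| Binomial(5, 0.75) | 31.5% | 6.84% | 6.17% | 5.04% | 8.61% |
| 4 | 34.7% | 6.57% | 5.92% | 4.99% | 8.55% |
| 5 | 46.2% | 6.64% | 6.03% | 4.96% | 9.65% |

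Repeat runs put the never-fitted figure at up to 9.8%. Among trials where the term is dropped, the error is about 9–10%. A 10% threshold gives 5.9–6.2% and a 20% threshold 5.3–5.6%. An ICC of 0.05 gives 6.1–6.4%, and 0.02 gives 5.3–5.6%.

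**Three-visit model.** 100,000 trials per setting, 4 or 5 patients, balanced ANOVA form, 28 df in both branches.

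| Municipality effect over time | Term | Kept | Rule | Always fitted |
|---|---|---|---|---|
| Linear | slope | at least 97% | 4.3–4.4% | 4.3% |
| Independent across visits | by time | 54–69% | 5.2–5.3% | 4.5–4.6% |
| Equal at 3 and 6 months | by time | 35–46% | 6.4–6.8% | 5.7–6.0% |

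The last two columns differ by 0–0.9 points, which is what the rule adds; the remainder is misfit of the term. Never fitting the term gives 6.3–9.0%. With a constant municipality level the error is 4.0–4.3%; with baseline as covariate only it is 1.4–5.7% (both on 28 df).

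**Power with the term always fitted.** Analysed patients per arm: 15 × 3.75 = 56.25. SE = √(2 × 2.83² × 1.275/56.25) = 0.603; 2/0.603 = 3.32; noncentral t on 28 df gives 0.893.

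**The case against.** The strongest reply is that the defect needs readings the protocol does not fix. Baseline PGSI is named as an adjustment variable, and the section also speaks of changes from baseline as dependent variables for RQ2. A model of 3- and 6-month values or changes with baseline as covariate is therefore possible, and there the unconditional municipality intercept carries the clustering. The ICC is not said to be that of change. The slopes may be patient slopes. The 32–46% figure comes from change scores, not from the planned repeated-measures model; when the municipality effect is truly linear in time, the slope is almost always kept and the rule costs nothing.

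Most of this stands, and it limits size and certainty. It does not remove the point. The interaction test favours baseline as a row, and the ICC stands beside an SD of change. If slopes are patient slopes only, no term carries municipality clustering of change, which is worse. Nor is this a detail merely left to the statistical analysis plan: the condition is written into the protocol, next to an unconditional claim that clustering is adjusted for.

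A reader might infer that the analysis ignores clustering, or that the error rate will be near 10%. The documents support neither. Municipality and patient effects are unconditional, and 8.5–9.8% applies on change scores only if the term is never fitted. A reader might also infer that the trial is too small; the power above shows otherwise.

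**Conclusion.** The point holds conditionally and is of minor to moderate severity. If baseline is an outcome row and the 10% ICC is that of change, the written rule can drop the planned clustering from the primary standard error, so the claim of correct adjustment is not secured. On change scores, with the assumed alpha and threshold, type I error is about 6.6–6.8% (about 6% with 28 df in both branches) against 5.0%. In three-visit models the rule itself adds 0–0.9 points, and nothing for a linear municipality effect. If either condition fails there is essentially no inflation. The case for acting is that the exposure is avoidable and the choice depends on the data, not that the expected error is large.

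**What to change.** Remove the significance condition for the municipality level, and state whether baseline PGSI is an outcome row or a covariate. Then use one of the following, with cluster-level (about 28) degrees of freedom:

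- Always include a municipality-by-time random effect with a single variance, besides the municipality and patient effects.
- Estimate the primary contrast from 3-month change (or the 3-month score) adjusted for baseline PGSI, with an unconditional municipality random intercept.

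The first keeps the three-visit model but gave 5.7–6.0% when the municipality effect was equal at 3 and 6 months. The second avoids assuming a shape over time; the unadjusted change-score version gave 5.0%. Simply making a linear municipality slope unconditional is not enough: it gave 6.9–7.9% when the effect was not linear. A municipality effect left unstructured across visits should not be required either, because its covariance estimate was not positive definite in about 41–84% of simulated trials.

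The cost is analysis wording only, with no extra patients. Standard errors are about 13–18% larger at ICC 0.10 than without the term, which the sample size already allows for. The municipality variance of change would be estimated as zero in roughly 7–14% of trials, so the plan should say what is done then (for example, keep 28 degrees of freedom).

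### Primary PGSI test: pairing the time-by-group interaction with baseline PGSI as a covariate gives either a modestly understated standard error under the planned dropout or a test that is not the 3-month contrast

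*Protocol*

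**What the plan says.** The Protocol section on baseline data and outcome measures defines the primary outcome as a between-arm difference in change in goal achievement, covering "challenges regarding crises between baseline and three months using the PGSI". Table 3 shows PGSI collected at baseline, 3 and 6 months.

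The section on data processing and statistical analysis for RQ1 and RQ2 specifies a "linear mixed model with fixed effects for time component and group and the interaction between the two". It reads the treatment effect from that interaction: "A significant interaction will imply the differences in change between the groups". On the random part it says: "Random effects for patients nested within municipalities and slopes (if significant) will be included into the model". It values the model for "allowing inclusion of all available information, also from dropouts". It then adds the covariates: "The analyses for primary and secondary outcomes will be adjusted for baseline PGSI-scores, baseline severity of dementia", together with age. The only other contrasts it names are within arms: "Individual time point contrasts will be derived within each group at each time point".

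The sample size section plans for "an estimated attrition rate of 25% for the primary outcome at three months".

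**The concern.** The section never says which visits are responses, and neither possibility gives a sound primary test as written.

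**Baseline is a response.** The interaction then measures change from baseline, as the text intends, but the same score is also a covariate with one coefficient for all visits. The covariate absorbs most of the between-patient variance, so the model treats a patient's visits as nearly uncorrelated. It then credits the baseline rows of dropouts with information on change that they do not carry, and the standard error comes out too small. The covariate also shrinks the baseline residuals more than the later ones. A random slope can fit that pattern, so the slope rule can bring in a slope that the covariate created.

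**Baseline is not a response.** The covariate is then proper, but the interaction is the 6-month arm difference minus the 3-month arm difference. The 3-month difference between arms can be read from the same model, but the plan does not name it.

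At stake are the confidence interval and p-value of the only primary test. RQ2 also takes forward outcomes found statistically significant, so a false positive would carry over.

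**Working it through.** **Plan's own figure.** The Protocol gives no standard error or error rate for this test, so there is none to reproduce. Its sample size is a separate matter: 32 per arm × 1.40 ÷ 0.75 ≈ 60 per arm, 120 in all at 80% power, against about 150 stated.

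**Inputs from the Protocol.** 30 municipalities of about 5 patients, 15 municipalities per arm; SD of change 2.83; ICC 10%; 25% loss by 3 months; effect 2 points.

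**Assumptions.** Two-sided 5% Wald test; random dropout with about 10% further loss by 6 months; equal variances and equal correlations over visits; baseline–follow-up correlation ρ of 0.3, 0.5 or 0.7. The score SD is 2.83/√(2(1−ρ)) = 2.39, 2.83 or 3.65, so 0.7 is less plausible on a 1–10 scale.

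**1. Anchor.** With an ICC on scores, the municipality effect cancels from change. Complete data, 75 per arm: SE = √(2 × 2.83²/75) = 0.462. Patients with a 3-month score only, 56.25 per arm: √(2 × 2.83²/56.25) = 0.534.

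**2. Simulation, ρ = 0.5, no true effect, 1000 trials, REML** (CDR and age left out)

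| Model | True SD | Mean SE | SE/SD | Type I error |
|---|---|---|---|---|
| Complete data, baseline as response and covariate | 0.453 | 0.461 | 1.02 | 4.1% |
| Dropout, response and covariate | 0.507 | 0.478 | 0.94 | 6.1% |
| Dropout, response only | 0.501 | 0.515 | 1.03 | 4.4% |
| Dropout, response and covariate, random slope added | 0.513 | 0.424 | 0.83 | 10.4% |
| Dropout, covariate only, 3-month arm difference | 0.474 | 0.492 | 1.04 | 4.3% |

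The complete-data SE matches the anchor. Cross-check: a ratio of 0.94 implies 2[1 − Φ(1.96 × 0.94)] ≈ 6.5%, and 0.82 implies 2[1 − Φ(1.96 × 0.82)] ≈ 10.8%. With a true 2-point effect, the double-use model under dropout has mean estimate 1.997, so there is no bias.

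**3. Range, random intercepts.** A larger set (2000 trials per ρ, CDR and age in the model) gave 6.4%, 7.1% and 7.6% for ρ = 0.3, 0.5 and 0.7. Over all its dropout settings the range was 6.2–8.8%, with the SE 6–10% too small. Other separately programmed runs gave 6.0–6.4%, 6.6%, 7.8–8.1% and 9.1%. Monte Carlo error is roughly 0.5–1 percentage point.

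**4. Slope rule.** A patient-level linear slope, correlated with the intercept, was kept if its likelihood-ratio test had p < 0.05. With the covariate it was significant in 100% of trials although no slope was simulated; without the covariate, in 2–3%. Type I error was 10.7%, 11.2% and 11.9%, with a range of 10.1–12.6% over dropout settings. The fit was singular in 100% of these trials. With complete data the rule still gave 7.8–8.6%.

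**5. ICC acting on change instead, ρ = 0.5, random intercepts**

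| Run | With covariate | Without covariate | Covariate only, 3-month difference |
|---|---|---|---|
| 1000 trials | 11.9% | 9.7% | 5.1% |
| 600 trials | 13.5% | 11.5% | 5.8% |

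The covariate adds 11.9 − 9.7 = 2.2 and 13.5 − 11.5 = 2.0 points. A further run of 920 trials gave 15.2% and 11.7%, a difference of 3.5. The rest of the excess comes from a missing municipality effect on change.

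**6. Baseline not a response.** If the arm difference is 2 points at both follow-up visits, the interaction is 2 − 2 = 0. In simulation it rejects in 5.4% of trials (ρ = 0.5), while the 3-month arm difference rejects in 98%.

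**The case against.** **Detail for the SAP.** The outcome section already names the estimand, and listing responses and contrasts is ordinary SAP content; the SAP is not at hand. This stands only in part: the Protocol itself fixes both the interaction test and the baseline adjustment, and it is this combination that fails.

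**The effect is small.** With random intercepts some runs show little more than 6%. A t test on 28 degrees of freedom lowers the 6.2–8.8% range to 5.1–7.6%. In a three-dataset check against other software, two random-intercept standard errors with the covariate differed, by 0.004 and 0.016 in opposite directions. If baseline varies half as much as follow-up (correlation 0.4 with baseline, 0.6 between follow-ups), the error is 8.9% with the covariate and 7.5% without. This stands: the excess is modest and its size depends on assumptions.

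**10–13% as the expected error rate.** A reader might infer this from the slope rule. The Protocol does not support it: it fixes neither the level of the slope nor its correlation with the intercept, and an analyst who rejects singular fits returns to the random-intercept figures.

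**Blaming the covariate for the whole excess when the ICC acts on change.** This is also tempting, since the sample size section pairs the ICC with an SD of change. Most of that excess is present without the covariate.

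**The plan would miss a sustained benefit.** That follows only if baseline is not a response, and the interaction sentence points the other way.

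**Conclusion.** The point holds as a fault in the stated primary analysis. On the reading that fits the text best, the interaction's standard error is about 6–10% too small and type I error about 6–9% with random intercepts. This rests on the planned attrition, ρ between 0.3 and 0.7 and the ICC acting on scores. Complete data with random intercepts show no fault. The 10–13% under the slope rule is conditional on accepting a singular patient-level slope fit. With the ICC acting on change, the covariate adds only about 2–3 points (3.5 in one run) to an error rate already at about 10–12%. On the other reading, the named test does not address the primary outcome.

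The documents do not support the inference that the treatment estimate is biased: under random dropout it is not. The correlation, the 6-month loss and the 5% level are assumptions, because the Protocol states none of them.

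**What to change.** State the responses, use baseline PGSI once, and name the primary contrast. Recommended: PGSI at 3 and 6 months as responses; arm, time, arm-by-time, baseline PGSI, CDR and age as fixed effects; random intercepts for municipality and patient; the between-arm difference at 3 months as the primary test. Its type I error was about 5% under both readings of the ICC (4.5–5.0% on scores in the 2000-trial set, 5.1–5.8% on change).

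Keeping baseline as a response, with a common mean in both arms and no baseline covariate, is acceptable only if a municipality effect on change is added to the random effects. Without that effect, type I error was 9.9% when the ICC acts on change (ρ = 0.5, 1000 trials).

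The cost is wording only, since PGSI is already collected at all three visits. The downside of the recommended form is that patients with no follow-up score do not contribute.
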